10.11	Pharmacokinetic and Antidrug Antibody Analyses.....	35
10.12	Correlative Analyses	35
11.	List of Planned Tables, Figures, Listings	35
11.1	Planned Tables	35
11.2	Planned Listings	40
11.3	Planned Figures	42

**Statistical Analysis Plan
SNDX-275-0602 (TRIO025)
DM-025-037**

List of Abbreviations

ADaM	Analysis Data Model
ADSL	Subject-level Analysis Dataset
AEs	Adverse Events
aTNBC	Advanced Triple Negative Breast Cancer
CBR	Clinical Benefit Rate
CI	Confidence Interval
CMH	Cochran-Mantel-Haenszel
CR	Complete Response
CTCAE	Common Terminology Criteria for Adverse Events
DLT	Dose-limiting Toxicity
DOOR	Duration of Response
DSMB	Data Safety Monitoring Board
ECG	Electrocardiogram
ECOG	Eastern Cooperative Oncology Group
eCRF	electronic Case Report Form
FAS	Full Analysis Set
FASFL	Full Analysis Set Population Flag
HER2	Human Epidermal Growth Factor Receptor 2
irRECIST	Immune-related RECIST
IDDI	International Drug Development Institute
IV	Intravenous
IWRS	Interactive Web Response System

**Statistical Analysis Plan
SNDX-275-0602 (TRIO025)
DM-025-037**

KM	Kaplan-Meier
MedDRA	Medical Dictionary for Regulatory Activities
MTD	Maximum Tolerated Dose
NCI	National Cancer Institute
NE	Not evaluable
ORR	Objective Response Rate
OS	Overall Survival
PD	Progressive Disease
PFS	Progression Free Survival
PO	per os (Oral Administration)
PPROTFL	Per-protocol Population Flag
PR	Partial Response
PT	Preferred Term
Q1	First Quartile (25 th percentile)
Q3	Third Quartile (75 th percentile)
RDI	Relative Dose Intensity
RECIST	Response Evaluation Criteria in Solid Tumors
RP2D	Recommended Phase 2 Dose
SAEs	Serious Adverse Events
SAFFL	Safety Population Flag
SAP	Statistical Analysis Plan
SD	Stable Disease
SOC	System Organ Class

**Statistical Analysis Plan
SNDX-275-0602 (TRIO025)
DM-025-037**

TEAEs	Treatment Emergent Adverse Events
TLF	Tables, Listings, and Figures
TRIO	Translational Research in Oncology
TTR	Time To Response
WHODD	World Health Organization Drug Dictionary

**Statistical Analysis Plan
SNDX-275-0602 (TRIO025)
DM-025-037**

Revision History

Not applicable; this is the initial version of Statistical Analysis Plan.

**Statistical Analysis Plan
SNDX-275-0602 (TRIO025)
DM-025-037**

1. INTRODUCTION

This Statistical Analysis Plan (SAP) describes the detailed statistical methodology for executing the statistical analyses to assess the antitumor activity and safety profile of atezolizumab in combination with entinostat versus atezolizumab alone in treatment of advanced triple negative breast cancer (aTNBC) according to SNDX-275-0602 (TRIO025) protocol version 1.0.

Statistical analysis will be performed by TRIO using SAS® software Version 9.3 which meets the requirement as stated in the protocol.

2. STUDY OBJECTIVES

2.1 Primary Objective

The primary objective for each phase of the study is as follows:

Phase 1b (Dose Determination Cohort): To determine the dose-limiting toxicities (DLT) and maximum tolerated dose (MTD) or recommended Phase 2 dose (RP2D) of entinostat (SNDX-275) given in combination with atezolizumab.

Phase 2 (Expansion Cohort): To perform an evaluation of the efficacy of entinostat at the RP2D in combination with atezolizumab in patients with aTNBC, as determined by the duration of progression-free survival (PFS) based on the local investigator's assessment of progressive disease Response Evaluation Criteria in Solid Tumors version 1.1 (RECIST 1.1).

2.2 Secondary Objectives

2.2.1 Efficacy

To evaluate the efficacy of entinostat in combination with atezolizumab in patients with aTNBC, as determined by:

- PFS based on immune-related RECIST (irRECIST)
- Overall response rate (ORR) (complete response [CR] or partial response [PR]) based on RECIST 1.1
- ORR (irCR or irPR) based on irRECIST
- Clinical benefit rate (CBR) (CR or PR or stable disease [SD] for at least 24 weeks) based on RECIST 1.1
- CBR (irCR, irPR or irSD for at least 24 weeks) based on irRECIST
- Overall survival (OS)

In patients with best overall response of CR or PR based on RECIST 1.1 and irCR or irPR based on irRECIST:

**Statistical Analysis Plan
SNDX-275-0602 (TRIO025)
DM-025-037**

- Duration of response (DOR)
- Time to response (TTR)

2.2.2 Safety

To evaluate safety and the tolerability of entinostat in combination with atezolizumab, as measured by clinical adverse events (AEs) and laboratory parameters.

2.3 Exploratory Objectives

The exploratory study objectives are to:

- [REDACTED]
- [REDACTED]
- [REDACTED].
- [REDACTED]
- [REDACTED]
- [REDACTED].
- [REDACTED]
- [REDACTED]
- [REDACTED]
- [REDACTED].
- [REDACTED]
- [REDACTED].

The exploratory objectives will be performed afterwards and detailed in a separate document(s).

3. STUDY DESIGN

**Statistical Analysis Plan
SNDX-275-0602 (TRIO025)
DM-025-037**

This is a Phase 1b/2 study evaluating the combination of entinostat plus atezolizumab in patients with aTNBC. The study has 2 phases: an open-label Dose Determination Phase (Phase 1b) followed by an Expansion Phase (Phase 2).

The Expansion Phase will evaluate the efficacy and safety of entinostat when administered at the RP2D with atezolizumab in patients with aTNBC in a randomized, double-blind, placebo-controlled setting.

3.1 Phase 1b Dose Determination Phase

This study phase employs a classical 3+3 design, with the determination of DLT and the MTD or RP2D at cycle 1 based on the combination of entinostat (at the dose of 5mg, 3mg or 2mg weekly) with atezolizumab at a fixed dose of 1200 mg iv. Six patients will need to be treated in a dose level for it to be considered MTD or the RP2D. The recommended dose for Phase 2 investigation will be the higher of either 2, 3, or 5mg weekly PO that results in less than a 33% incidence of DLT.

Note: Based on evaluation of the safety and tolerability data gathered during the dose determination phase together with data from other clinical trials, it may also be decided that accrual will take place at an alternate dose level or dosing schedule via a protocol amendment.

Up to 18 patients are expected to be enrolled in the Dose Determination Phase of the study.

3.2 Phase 2 Expansion Phase

The phase 2 expansion phase is a randomized, multicenter, double-blind, placebo-controlled study phase. Randomization for this portion of the study is stratified by geographic location (US vs. rest of world).

70 eligible patients are randomly assigned in a 1:1 ratio to either:

- Entinostat per os (p.o.) weekly at the RP2D combined with atezolizumab at a fixed dose of 1200 mg iv every 3 weeks**

OR

- Placebo combined with atezolizumab at a fixed dose of 1200 mg iv every 3 weeks**

Patients will follow the same schedule of study visits and assessments as specified in the Dose Determination Phase (with the exception of the tumor tissue biopsy at C2D15). Patients may

**Statistical Analysis Plan
SNDX-275-0602 (TRIO025)
DM-025-037**

continue study treatment until documented progressive disease, intolerable toxicity or meets one of the study withdrawal criteria (Protocol Section 11).

Patients will be followed for overall survival (OS) until death (due to any cause) or the Sponsor terminates the trial.

4. STUDY ENDPOINTS

4.1 Phase 1b Dose Determination Phase

The primary endpoint of the Phase 1b Dose Determination portion of the study is the determination of the DLT, MTD or RP2D of entinostat in combination with atezolizumab at the dose of 1200mg .

The following safety endpoints will also be assessed:

- AEs
- Clinical laboratory parameters, vital signs, physical examinations, and ECGs

Exploratory endpoints will also be assessed [REDACTED] and are discussed in a separate SAP.

4.2 Phase 2 Expansion Phase

4.2.1 Primary Efficacy Endpoint

The primary efficacy endpoint is PFS as determined by the local investigator using RECIST 1.1.

4.2.2 Secondary Efficacy Endpoints

- PFS determined by the local investigator using irRECIST
- ORR (CR or PR) by RECIST 1.1
- ORR (irCR or irPR) by irRECIST
- CBR (CR, PR or SD for at least 24 weeks) by RECIST 1.1
- CBR (irCR, irPR, or irSD for at least 24 weeks) by irRECIST
- OS

In patients who experience a response to treatment based on RECIST 1.1 (CR or PR) or on irRECIST (irCR or irPR):

- DOR
- TTR

**Statistical Analysis Plan
SNDX-275-0602 (TRIO025)
DM-025-037**

4.2.3 Safety

Safety endpoints are:

- AEs
- Clinical laboratory parameters, vital signs, physical examinations, and ECGs

4.2.4 Exploratory

The exploratory endpoints will be discussed in separate SAP(s).

5. STATISTICAL CONSIDERATIONS

5.1 Hypothesis for Phase 2

The primary efficacy analysis will be the comparison of the distribution of PFS between the two treatment groups using a stratified logrank test at one-sided 10 % level of significance, i.e.:

H_0 : PFS in experimental arm (entinostat + atezolizumab) = PFS in control arm (placebo + atezolizumab)

vs.

H_a : PFS in experimental arm (entinostat + atezolizumab) > PFS in control arm (placebo + atezolizumab)

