13.1.2 Expansion Phase

The Expansion Phase will evaluate the efficacy and safety of entinostat when administered at the recommended Phase 2 dose with atezolizumab in a randomized, double-blind, placebo-controlled setting. Up to 70 eligible patients with metastatic TNBC will be randomized to receive atezolizumab with entinostat or placebo in a 1:1 allocation.

The true median PFS for patients with aTNBC receiving atezolizumab monotherapy is expected to be approximately 4 months from the initiation of such treatment. It is hypothesized that the combination of entinostat and atezolizumab will improve true median PFS by 3 months (i.e., from 4 to 7 months). Under the exponential distribution, such an improvement in median PFS represents a reduction of 43% for the true PFS failure hazard rate or equivalently, a hazard ratio of 0.57. Inferential comparisons will be performed using a stratified log-rank test, stratifying on the randomization stratification factor of geographic location. Total information of 60 PFS failures, defined as documented progressive disease by RECIST 1.1 or death due to any cause

without documented progressive disease beforehand, is estimated to provide 80% power to detect a 43% reduction in the PFS failure hazard rate with 1-sided significance level of 0.1 (SEQDESIGN procedure, SAS version 9.2).

Assuming approximately 9 months of accrual and an additional 9 months of follow-up, total accrual of 70 patients (approximately 35 per treatment arm) is projected to result in 60 PFS failures within approximately 18 months of the first patient randomization. Patients who discontinue study treatment for reasons not due to documented progressive disease by RECIST 1.1 will continue to undergo disease assessments until the earlier of documented progressive disease, death, or withdrawal of consent/lost to follow-up. It is anticipated that the number of patients who will drop out of the study without PFS failure beforehand will be low (2–3%). Depending on the actual number of such dropouts, the number of patients accrued may be increased by 6–10 additional patients to accommodate for a higher-than-expected number of dropouts.

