13.2 Phase 2 Interim Efficacy Analyses

The sample size and number of PFS failures were adjusted using the O'Brien -Fleming group sequential procedure to account for 1 planned interim analysis of PFS after 45 events (75% information). It is projected that 75% and 100% of total information will be reported at approximately 12 and 18 months, respectively.

The interim analysis will be performed to support the Sponsor's product development plans and ongoing resourcing activities. Although there are no plans to terminate the study early because of early evidence of superior efficacy for the combination treatment, the significance levels at the interim analysis and final analysis will be adjusted to maintain control of the overall type I error rate for multiple testing of PFS (O'Brien 1979).

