13.5.5 Efficacy Analyses

Efficacy analyses will be conducted using the Full Analysis Set and, where appropriate, the Per-protocol Set. With the exception of PFS, all hypothesis testing will be assessed using a one-sided significance level of 0.1. The Lan-DeMets alpha spending function with an O'Brien-Fleming type boundary will be used to control the overall type I error for multiple testing of PFS. The boundary will be derived based on the actual number of PFS failures reported for each analysis.

The primary efficacy endpoint is duration of PFS, defined as the number of months from randomization to the earlier of progressive disease or death due to any cause. Disease assessments will continue until progressive disease, even after the originally assigned study treatment is discontinued. For purposes of analysis, one month is considered 30.4375 days.

The duration of PFS will be summarized descriptively using the Kaplan-Meier method with 95% confidence intervals calculated using Greenwood's formula. Inferential comparisons between treatment arms will be made using the stratified log rank test, stratifying on the randomization stratification factor of geographic location. Estimation of the hazard ratio for treatment effect and its corresponding 95% confidence interval will be determined using a stratified Cox proportional hazards model, without any other covariate. Homogeneity in the hazard ratios between randomization strata will be examined by Wald's test. The corresponding results without stratification will be reported as supplemental analyses. The adequacy of the Cox model will be evaluated, including an assessment of the proportional hazards assumption ([Therneau 2000](#)).

For the interim and primary analyses, PFS will be right-censored for patients who meet one or more of the following conditions:

- Patients with no screening or post-screening disease assessments unless death occurred prior to the first planned assessment (in which case the death will be considered a PFS event)
- Patients who initiate subsequent anticancer therapy in the absence of documented progression
- Patients who die or have progressive disease after missing 2 or more consecutively scheduled disease assessment visits
- Patients who are last known to be alive and progression-free on or before the data cut-off date

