5.2.2 Phase 2 Expansion Phase

The following assumptions are made:

- Patients in the control arm have true median PFS of 4 months
- Patients in the experimental arm have true median PFS of 7 months (under exponential distribution, true PFS hazard ratio of 0.57)
- Expected accrual duration will be 9 months and an additional 9 months of follow-up. The α type I error rate is set to 10% (1-sided)
- The β type II error rate is set to 20% (i.e. the power of the trial will be 80%)

Under these assumptions, 70 patients (35 per arm) will be enrolled in the trial, which is projected to result in 60 PFS failures, defined as documented disease progression by RECIST 1.1 or death due to any cause without documented disease progression beforehand, within approximately 18 months of the first patient randomized.

It is anticipated that the number of patients that drop out without PFS failure will be low (2-3%). Depending on the actual number of such dropouts, the number of patients accrued maybe increased by 6-10 patients to accommodate for a higher-than-expected number of dropouts.

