5.4.2 Phase 2 Expansion Phase

The following analyses are planned:

- An interim safety analysis will be performed following the completion of Cycle 1 for the first 20 patients enrolled in the Phase 2 expansion phase, and will utilize a Data Safety Monitoring Board (DSMB).
- An interim efficacy analysis will be performed when 45 PFS events have observed. Data cut-off for the analysis will be based on the calendar date of the 45th PFS event (per RECSIT 1.1). Safety and secondary endpoints will also be evaluated. The same data cut-off used for the PFS analysis is also used for the corresponding analysis of safety and secondary endpoints.
- Primary efficacy analysis will be performed when 60 PFS events are observed. Similarly, the data cut-off for the primary analysis will be based on the calendar date of the 60th PFS event. Safety and secondary endpoints will coincide with the primary PFS analysis.
- End of study analysis for safety and OS analysis will be performed when the last patient terminates study treatment.

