8. INTERIM ANALYSIS AND EARLY STOPPING RULE

One interim safety analysis is planned during the Phase 2 of the study after the first 20 patients are treated for one cycle. As mentioned in section 5.3.2, the result of this analysis will be reviewed by DSMB who will act in an advisory capacity to the Sponsor with respect to safeguarding the interests of trial patients and assessing the safety of the interventions administered during the trial. As per Section 13.2 of the protocol, an interim efficacy analysis is performed when 45 PFS events are observed to support the Sponsor's product development plans and ongoing resourcing activities. Although there are no plans to terminate the study early, the DSMB will review the results and decision will be made in collaboration with the Sponsor as well as the Steering Committee should the study needs to be terminated.

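### The SAP tests the primary PFS endpoint at an unadjusted one-sided 10%, while the protocol's interim adjustment implies a final level of about 0.084

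*SAP*

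**What the plan says.** **SAP.** Section 5.1 sets the primary comparison of PFS "using a stratified logrank test at one-sided 10 % level of significance". Section 5.2.2 uses the same one-sided 10% as the design's type I error rate. Section 5.4.2 schedules an interim efficacy analysis at 45 PFS events and then states: "Primary efficacy analysis will be performed when 60 PFS events are observed". Section 8 cites protocol 13.2 as the basis for the interim, repeats that early termination is not planned, but adds that after DSMB review a "decision will be made in collaboration with the Sponsor as well as the Steering Committee should the study needs to be terminated". Section 10.8.1 specifies the stratified log-rank test and the Cox model and gives no significance level. None of sections 5.1, 5.2.2, 5.4.2, 8 or 10.8.1 contains a boundary, a spending function or an adjusted level.

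**Protocol.** Section 13.1.2 says that 60 PFS failures "is estimated to provide 80% power to detect a 43% reduction in the PFS failure hazard rate with 1-sided significance level of 0.1". Section 13.2 says the event number was adjusted for one interim at 45 events (75% information) and that "the significance levels at the interim analysis and final analysis will be adjusted to maintain control of the overall type I error rate". Section 13.5.5 states: "With the exception of PFS, all hypothesis testing will be assessed using a one-sided significance level of 0.1". For PFS it names Lan-DeMets spending of O'Brien-Fleming type and adds: "The boundary will be derived based on the actual number of PFS failures reported for each analysis".

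**The concern.** As written, the SAP gives PFS the one level that protocol 13.5.5 says does not apply to PFS. A programmer working from SAP 5.1 and 10.8.1 would compare the final p-value with 0.10; one working from the protocol would compare it with a smaller, event-dependent value. The two documents would then disagree on whether the primary endpoint was met for any result between those thresholds, and the disagreement would surface only after unblinding.

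There is also a question of error control. If a positive interim can be claimed as a success and the final is then tested at the full 10%, the overall type I error exceeds 10%.

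**Working it through.** **Inputs.** Overall one-sided alpha 0.10, power 80% and medians of 4 and 7 months, so HR = 4/7 (protocol 13.1.2, SAP 5.2.2); 1:1 allocation; looks at 45 and 60 events, information fraction t = 45/60 = 0.75 (protocol 13.2, SAP 5.4.2); spending rule from protocol 13.5.5. The interim and final log-rank statistics are treated as bivariate normal with correlation √0.75.

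**1. Reproduce the plan's 60 events.**
- Fixed test at one-sided 0.10: events = 4(z₀.₉₀ + z₀.₈₀)² / (ln HR)² = 4(1.2816 + 0.8416)² / (ln 4/7)² = 57.6.
- With the Lan-DeMets boundary and one look at t = 0.75: 59.7 events (59.2 at HR 0.57).
- The planned 60 therefore fits the adjusted design, and 10% was its overall alpha.

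**2. Nominal levels under the protocol's rule.**
- Interim spend: 2 − 2Φ(z₀.₉₅/√0.75) = 2 − 2Φ(1.899) = 0.0575, boundary z = 1.576.
- Final: solve P(Z₁ > 1.576 or Z₂ > c) = 0.10 under the null. This gives c = 1.380, nominal one-sided p = 0.0839.
- The classical O'Brien-Fleming procedure cited in protocol 13.2 gives 0.0563 and 0.0847, so either protocol wording leads to a final level of 0.084 to 0.085.

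**3. Critical hazard ratio at 60 events,** exp(−2z/√60):

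| Rule | z | One-sided p | Critical HR |
|---|---|---|---|
| Protocol (Lan-DeMets) | 1.380 | 0.0839 | 0.700 |
| SAP 5.1 as written | 1.2816 | 0.10 | 0.718 |

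**4. Sensitivity to interim timing.** With the final at 60 events and the interim at 40, the final level is 0.0874 (z = 1.357, HR 0.704). With the interim at 50, it is 0.0806 (z = 1.401, HR 0.696).

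**5. Probability that the rules disagree.** At HR 4/7 the final statistic has mean |ln(4/7)| × √(60/4) = 2.167.
- Interim cannot count as success, P(1.2816 < Z₂ < 1.380): 0.100 − 0.0839 = 1.6% under the null; 0.812 − 0.785 = 2.8% at HR 4/7 (from unrounded values).
- Interim crossing counts under both rules, so some of these trials have already succeeded at 45 events: 1.3% under the null and 2.2% at HR 4/7.

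**6. Type I error with the final tested at 0.10.**
- Interim cannot count as success: 10%.
- Interim counts at the protocol's boundary (z = 1.576): 11.3%.

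**7. Power at HR 4/7, 60 events.** Both looks with the adjusted boundary, 80.1%; final test alone at 0.0839, 78.5%; final test alone at 0.10, 81.2%.

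**The case against.** The best counter-argument is that this is an omission and not a conflict. Protocol 13.1.2 itself quotes a one-sided 0.1 without qualification where it plainly means overall alpha; SAP 5.2.2 calls 10% the type I error rate; and the 60 events match the adjusted design. SAP 8 also cites protocol 13.2, where the adjustment is stated, and no SAP text claims to override the protocol. A statistician holding both documents could find the rule.

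Much of this stands as an account of what was probably intended. It does not settle what the SAP instructs. Section 5.1 attaches 10% to the test, and even if 10% is read as overall alpha, the SAP supplies no level or method for the final comparison. The citation in section 8 covers the conduct and purpose of the interim, not the adjustment.

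Three further points are fair. The protocol does not print 0.084; it follows from the rule at 45 and 60 events. The SAP is written to protocol version 1.0, so this comparison is with the protocol supplied and cannot show whether the SAP departed from the version it cites. And neither document plans to stop early for efficacy, so the 11.3% is conditional. The absence of a planned stop does not waive the adjustment, however: protocol 13.2 states both in the same sentence.

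**Conclusion.** The concern holds and should be fixed. The two documents give different decision thresholds for the primary endpoint: a one-sided 0.10 in the SAP as written, and about 0.084 under the protocol's rule. The latter assumes looks at exactly 45 and 60 events; with the final at 60, it runs from 0.087 to 0.081 for an interim at 40 to 50 events.

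The practical effect is modest. The rules disagree in roughly 1% to 3% of trials, depending on the true effect and on whether the interim can count. Type I error is inflated, to 11.3%, only if an interim crossing can be claimed as success; otherwise it stays at 10% and the problem is departure from the prespecified rule.

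**What to change.** In SAP 5.1, 8 and 10.8.1, state that 10% is the overall one-sided alpha for PFS. Carry over the rule in protocol 13.5.5: Lan-DeMets spending of O'Brien-Fleming type, with the boundary recomputed from the PFS events actually observed at each analysis. Give the nominal levels at 45 and 60 events (about 0.0575 and 0.084) as illustration only. No interim success declaration or stopping rule should be added.

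The cost is SAP wording; no patients or events are added. The final threshold becomes slightly stricter. The planned 80% power is kept when an interim crossing counts (80.1%). If only the final test counts, power is 78.5%, against 81.2% for a final test at 0.10.
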